**DEFINITION OF TERMS**

Active vaccines	Ad26.RSV.preF
	Nimenrix
Study vaccine	Ad26.RSV.preF or Control

## 1. INTRODUCTION

An independent data monitoring committee (IDMC) will be established in the study VAC18194RSV2002 to review safety data and to ensure the continuing safety of the subjects enrolled in this study.

This statistical analysis plan (SAP) contains the derivations and statistical methods for the analysis to be conducted for the IDMC. There is one planned IDMC analysis in the current study, to be performed on Day 8, after the first dose in the first 12 toddlers (6 receiving the active vaccine and 6 receiving placebo). Snapshot data will be used—The database will be cleaned on an ongoing basis, there will be no formal data cleaning for the IDMC analyses.

The IDMC will review unblinded data. An external statistician (the statistical support group (SSG) statistician) independent of the sponsor and not involved in the interim, primary, and final analyses of the study will prepare the data and perform all analyses for review by the IDMC .

Details on each table, graph and listing to be generated for the IDMC is described in a separate data presentation specifications (DPS) document. However, the study team or IDMC may request additional deliverables, with this SAP serving as a guidance. Safety data from the interim (if applicable), primary and final analyses will also be shared with the IDMC.

### 1.1. Objectives of the IDMC

The primary purpose of this IDMC is to ensure the safety of subjects in this study by monitoring safety data collected in the clinical program and to provide recommendations to the study team. Special attention will be given to severe RSV-LRTI cases. The IDMC will make recommendations regarding the conduct of the study including changes to the informed consent. Details on the roles and responsibilities of the IDMC are described in Section 5 of the IDMC charter.

### 1.2. Trial Design

This is a multi-center, randomized, observer-blind, Phase 1/2a study, to be conducted in 48 male and female RSV-seronegative toddlers aged  $\geq 12$  to  $\leq 24$  months.

Each subject's RSV serostatus will be assessed by RSV enzyme immunoassay (EIA) at screeninga. *Note:* serostatus may be assessed via this assay if available from a different study of the sponsor (VAC18194RSV2001). If done within 42 days of first dose, this assessment would not have to be repeated in the absence of a history of respiratory infection during that period. Additionally, the seronegative status will be confirmed by the absence of an anamnestic humoral immune response (which is usually observed 7-10 days post antigen re-exposure in RSV seropositive subjects) from blood samples taken on Day 8 after the first dose.

---

a The cut-off for seronegativity is a titer  $<1$  EIA unit.

Subjects will be randomized 1:1 to receive either Ad26/Ad26/Ad26 (at  $2.5 \times 10^{10}$  vp) or placebo/placebo/Nimenrix®a,b (or placebo/placebo/placebo) (Table 1).

**Table 1: Study Design VAC18194RSV2002**

Group	N	Day 1	Day 29/Week 4	Day 57/Week 8
RSV-seronegative toddlers 12 to 24 months				
Group 1	24	Ad26.RSV.preF ( $2.5 \times 10^{10}$ vp)	Ad26.RSV.preF ( $2.5 \times 10^{10}$ vp)	Ad26.RSV.preF ( $2.5 \times 10^{10}$ vp)
Group 2	24	Placebo (saline)	Placebo (saline)	Nimenrix or Placebo (saline)

N = number of subjects; vp = viral particles

Subjects will be followed up for safety up to 2 RSV seasons after the first dose. Immunogenicity samples will be taken at Day 1, Day 8, Day 85 and at the end of the first RSV season. For safety, solicited AEs will be checked up to Day 8 after each vaccination, unsolicited AEs up to Day 85 and SAEs throughout. All RTIs will be collected during the RSV season. Severe LRTIs and medically-attended RTIs (MA-RTIs) will be collected throughout the whole study.

For more details on the design, refer to the clinical trial protocol (CTP), section 3.1.

### 1.3. Statistical Hypotheses for Trial Objectives

No formal statistical hypothesis will be tested.

### 1.4. Sample Size Justification

See CTP, Section 11.2.

### 1.5. Randomization and Blinding

See CTP, Section 5.

a In countries where the commercial vaccine Nimenrix is licensed, placebo (0.9% saline) can be replaced with Nimenrix as the Day 57 vaccination for the study subjects in the control group, in accordance with the local label and local regulations, and unless contra-indicated. Nimenrix will be administered, only if permitted by the subject's parent/legal guardian and following PI assessment on a case-by-case basis as vaccination with Nimenrix outside this study might be preferred (joint parent/legal guardian and PI decision). In the US, Nimenrix will not be used unless it has been licensed for use or an IND has been submitted. It should be recorded in the eCRF by the unblinded pharmacist whether the subject was vaccinated with either Nimenrix or placebo on Day 57.

b Nimenrix is a vaccine used to protect adults, adolescents, and children from the age of 6 weeks against invasive meningococcal disease caused by 4 groups of the bacterium *Neisseria meningitidis* (group A, C, W-135, and Y).

## 2. GENERAL ANALYSIS DEFINITIONS

A baseline (or reference) value will be defined as the value of the last available assessment performed prior to the first dose (active vaccine or placebo).

### 2.1. Study Phases

The phases and periods in the study will be constructed as follows:

**Table 2: Analysis Phases and Periods**

Phase	Phase #	Period	Period #	Interval	
				From	To
Screening	1			Date and time of signing the informed consent form a	One minute prior to first vaccination
Regimen	2	Post-dose 1	1	Date and time of first vaccination	Minimum of: a) 23:59 at the date of last contact (for early discontinuation) b) 23:59 at the date of database cut-off date in case of interim analysis c) One minute prior to second vaccination. If second vaccination was not administered, then use maximum of (Day 28 after the first vaccination at 23:59, scheduled visit 28 days after first vaccination at 23:59)
Regimen	2	Post-dose 2	2	Date and time of second vaccination	Minimum of: a) 23:59 at the date of last contact (for early discontinuation) b) 23:59 at the date of database cut-off date in case of interim analysis c) One minute prior to third vaccination. If third vaccination was not administered, then use maximum of (Day 28 after the second vaccination at 23:59, scheduled visit 28 days after second vaccination at 23:59)
Regimen	2	Post-dose 3	3	Date and time of third vaccination	Minimum of: a) 23:59 at the date of last contact (for early discontinuation) b) 23:59 at the date of database cut-off date in case of interim analysis c) Maximum (Day 28 after the third vaccination at 23:59, scheduled visit 28 days after third vaccination at 23:59)
Follow-up	3			One minute after the end of the last post-dose period	Minimum of: a) 23:59 at the Date of last contact b) 23:59 at the date of database cut-off date in case of interim

a In case an earlier date is available (e.g. for vital signs), then use the very first date to include all data in the screening phase.

Adverse events will be allocated to the above phases and periods, see details in section 4.1. The regimen phase (post-dose 1, post-dose 2 and post-dose 3 periods) is considered the active phase, the screening and follow-up phase are considered non-active phases.

For descriptive statistics over time, assessments (regardless of the investigated parameter) will be allocated to an analysis visit based on the planned visit as captured in the database.

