An IDMC has been established for the ongoing study VAC18194RSV2001 in RSV-seropositive toddlers and all subsequent studies with Ad26.RSV.preF in children (including the current study), to evaluate safety and reactogenicity data on a regular basis. See Section 11.9.2 for details.

An independent, blinded CEC has been established for ongoing study VAC18194RSV2001 in RSV-seropositive toddlers and all subsequent studies with Ad26.RSV.preF in children (including the current study), to assess suspected cases of severe LRTI and the occurrence of RSV infection. See Section 11.9.1 for details.

The study will have 3 phases: a **screening phase**, a **vaccination phase**, and a **safety follow-up phase** through 2 RSV seasons after the first dose. The durations of the respective phases are as follows:

^k In countries where the commercial vaccine Nimenrix is licensed, placebo (0.9% saline) can be replaced with Nimenrix as the Day 57 vaccination for the study subjects in the control group, in accordance with the local label and local regulations, and unless contra-indicated. Nimenrix will be administered, only if permitted by the subject's parent/legal guardian and following PI assessment on a case-by-case basis as vaccination with Nimenrix outside this study might be preferred (joint parent/legal guardian and PI decision). In the US, Nimenrix will not be used unless it has been licensed for use or an IND has been submitted. It should be recorded in the eCRF by the unblinded pharmacist whether the subject was vaccinated with either Nimenrix or placebo on Day 57.

¹ Nimenrix is a vaccine used to protect adults, adolescents, and children from the age of 6 weeks against invasive meningococcal disease caused by 4 groups of the bacterium *Neisseria meningitidis* (group A, C, W-135, and Y).¹²

Phase	
Screening:	up to 6 weeks before the first dose
Vaccination:	34 weeks 
 • dosing on Days 1, 29 and 57 • safety follow-up through 6 months post-final dose • immunogenicity at: 
 ➤ pre-Dose 1 (Day 1) ➤ 7 days post-Dose 1 (Day 8) ➤ 28 days post-Dose 3 (Day 85) ➤ end of the first RSV season post-first dose
Safety follow-up:	through 2 RSV seasons after the first dose

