10.3. Contraindications to Vaccination

The following events constitute a contraindication to vaccination at that point in time:

- Severe acute illness at the time of vaccination. This does not include minor illnesses such as diarrhea.
- Fever (body temperature ≥ 38.0 °C) at the time of vaccination.

If any of these events occur at the scheduled time for the first vaccination, enrollment at a later date is permitted^{cc} at the discretion of the investigator and after consultation with the sponsor. If any of these events occur at the scheduled time for the second or third vaccination, the subject may be vaccinated up to 10 days beyond the scheduled vaccination, or be withdrawn from further vaccination at the discretion of the investigator and after consultation with the sponsor. In the event of an ongoing AE or other situation precluding subject vaccination within 10 days, subjects may be vaccinated beyond the 10-day window at the discretion of the sponsor.

Note: Medically-indicated vaccines should be given at least 14 days before or 14 days after study vaccine administration. If a vaccine is indicated in a post-exposure setting (eg, rabies or tetanus), it must take priority over the study vaccine (see Section 4.3).

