11.1. Analysis Sets

Vaccination assignment will follow the as-treated principle.

^{cc} If within the screening window. Otherwise, rescreening is required.

The Full Analysis (FA) set includes all subjects who were randomized and received at least one dose of study vaccine, regardless of the occurrence of protocol deviations. All safety analyses will be based on the FA set. As a sensitivity analysis, key immunogenicity tables will also be based on the FA set.

The Per-protocol Immunogenicity (PPI) analysis set will include all randomized and vaccinated subjects for whom immunogenicity data are available, excluding subjects with major protocol deviations expected to impact the immunogenicity outcomes. Any subject with an anamnestic response at Day 8 will not be included in the PPI analysis set.

In addition, the following samples will not be included in the PPI set:

- If subjects miss one or more doses, but continue the planned visit schedule, samples taken after the planned but missed dose(s) will not be taken into account;
- For subjects who experience a natural RSV infection (based on RT-PCR, or other sources), samples taken after the natural infection will not be taken into account.

The analysis of immunogenicity will be based on the PPI set.

Additionally, a modified intent-to-treat (mITT) analysis set is defined as a subset of the FA set excluding subjects who are seronegative at screening but for whom there is an anamnestic response at Day 8. The criteria for assessment of the anamnestic response will be specified in the SAP. The mITT set will be the primary analysis set for assessment of RSV infection in seronegative subjects.

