## 4. SAFETY

Continuous variables will be summarized using the following statistics, as appropriate: number of observations, arithmetic mean (mean), 95% CI for the mean, standard deviation (SD), standard error (SE), median, quartiles (Q1 and Q3), minimum and maximum. Frequencies and percentages (to one decimal place) will be generated for categorical variables.

Safety data will be summarized in each period of the active phase. Only SAEs will be tabulated for all phases, including the non-active phases. The analysis phases are defined in section 2.1. Denominator for the percentages is the number of subjects in the considered population and period for a certain regimen (incidence per 100 subjects/period).

*Note:* Safety data post-dose 3 in the control group will be presented separately for Nimenrix and placebo, unless otherwise specified (section 5.2).

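### In the IDMC SAP, Table 2 puts the weeks between a missed dose 2 and a given dose 3 in no analysis phase, so an SAE starting then would be absent from the phase-based SAE tables

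*SAP*

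**What the plan says.** SAP section 2.1, Table 2, divides each child's time into Screening, three post-dose periods and Follow-up.

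- Post-dose 1 normally ends one minute before the second vaccination. For a missed second dose the rule is "If second vaccination was not administered, then use maximum of" two limits: Day 28 after dose 1 and the scheduled 28-day visit, each taken at 23:59.
- Post-dose 2 begins at the second vaccination, so it does not exist for a child who never received one.
- Post-dose 3 begins at "Date and time of third vaccination".
- Follow-up begins "One minute after the end of the last post-dose period".

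Step 1 of the allocation rules in SAP section 4.1.1 attributes an event to a period when its start lies within that period. The other provisions there deal only with partial or missing dates. On scope, SAP section 4 says "Only SAEs will be tabulated for all phases, including the non-active phases", and section 4.1.1 says SAEs are to be presented over the whole study.

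The protocol plans "dosing on Days 1, 29 and 57" (section 3.1). Section 11.1 foresees missed doses, in a rule on which immunogenicity samples to exclude: "If subjects miss one or more doses, but continue the planned visit schedule".

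**The concern.** The phases should cover all time from first vaccination to last contact, because the SAE tables are built from them and SAEs from first dose to end of study are a primary endpoint. For one dosing pattern, dose 2 missed and dose 3 given, they do not. A fully dated SAE in the uncovered interval matches no row of Table 2, and nothing would signal that the table count was short. In a trial of 36 planned toddlers, a single SAE missing from a table shown to the IDMC would matter.

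Concomitant therapies are allocated to the same periods (SAP section 3.3), so a therapy taken wholly within the interval is affected in the same way. Non-serious unsolicited events are little affected, because only those starting within 28 days of a vaccination are tabulated.

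**Working it through.** The plan gives no figure on this point, so there is none to reproduce. The check is whether the Table 2 rules cover all time after dose 1.

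**Inputs**
- Nominal dosing on Days 1, 29 and 57 (Protocol 3.1).
- 28-day visit on Day 29 ± 3, and third vaccination ± 3 days (Protocol Time and Events Schedule and 9.1.2).
- Delay at the second or third vaccination: "the subject may be vaccinated up to 10 days beyond the scheduled vaccination" (Protocol 10.3), with longer delay at the sponsor's discretion.
- Assumptions: vaccination at 10:00. Because the schedule times vaccination 3 from vaccination 2, the windows for dose 3 are applied around nominal Day 57 when dose 2 is absent.

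**Coverage under five dosing patterns**

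| Pattern | Time in no phase |
|---|---|
| All three doses given | 0 |
| Dose 2 delayed 10 days (Day 39), dose 3 on Day 67 | 0 |
| Dose 3 missed | 0 |
| Doses 2 and 3 missed | 0 |
| Dose 2 missed, dose 3 on Day 57 | 27.4 days |

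**Length of the gap**

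The gap runs from 00:00 on the day after post-dose 1 ends to the time of dose 3.

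- Nominal: post-dose 1 ends on Day 29 at 23:59. Days 30 to 56 are uncovered: 56 − 30 + 1 = 27 whole days. Adding the 10 hours before dose 3 on Day 57 gives 27 + 10/24 = 27.4 days. It makes no difference whether Day 28 after vaccination is counted as study Day 28 or 29, because the Day 29 visit sets the later limit.
- Shortest: visit on Day 32, dose 3 on Day 54. Days 33 to 53 = 21 whole days, or 21.4 days.
- Longest with a 10-day delay: visit on Day 29, dose 3 on Day 67. Days 30 to 66 = 37 whole days, or 37.4 days.

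**Fate of an SAE on, say, Day 40**

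It starts after post-dose 1 has closed, there is no post-dose 2, it precedes post-dose 3, and it precedes Follow-up. Its start date is complete, so the partial-date rules do not apply. It enters no phase-based table.

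**Expected number of affected SAEs**

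The documents give neither the number of children with this pattern nor an SAE rate. Assume 1 to 3 such children among the 37 enrolled at Amendment 6, and 0.1 to 0.3 SAEs per child-year.

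- Low: 1 × 27/365 × 0.1 = 0.007
- High: 3 × 27/365 × 0.3 = 0.067

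**The case against.** The strongest answer is that the triggering pattern may never occur. When a child cannot be vaccinated as scheduled, the protocol offers delay or withdrawal (sections 9.1.3.2.1 and 10.3), and a child discontinued from study vaccination receives no further dose (10.2). A reader might infer from section 11.1 that the protocol expects children to miss dose 2 and then receive dose 3. It does not say so. That text concerns continued visits and excluded samples, and a child who stops dosing after dose 1 but keeps attending fits it without creating any gap. This part of the objection stands, though no passage rules the pattern out.

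A reader might also infer that the SAE would go unseen. It would not. SAEs reach the sponsor within 24 hours (Protocol 12.3.2), a vaccine-related SAE triggers an IDMC meeting (11.10), and the SAP's listings and narratives for children with an SAE carry no phase condition (4.1.2). The loss is confined to phase-based table counts.

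The reach is limited too. This SAP serves the IDMC, with one planned analysis, triggered at Day 8 after dose 1 in the first 12 toddlers. Slow recruitment could put some of those children beyond Day 29 by then, but that review concerns 7-day data after dose 1. No SAP for the primary and final analyses is among the documents, so they do not support a claim that the primary-endpoint SAE tables themselves are wrong. Table 2 still defines periods through dose 3 and Follow-up, and the SAP is to guide additional IDMC requests.

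Finally, rule 1 for overlapping events (section 4.1.1, Step 2) names Follow-up as a phase that can precede an active phase. That suggests time between doses was meant to be Follow-up, but Table 2 does not define it that way.

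**Conclusion.** Table 2 is wrong as written for one dosing pattern. For a child who misses dose 2 and receives dose 3, about four weeks (27 days nominally, 21.4 to 37.4 days across the windows and a 10-day delay) belong to no phase. A fully dated SAE starting then would be missing from the phase-based SAE tables, contrary to the SAP's stated intent.

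The practical size is small. The expected number of such SAEs is well below one, and it rests on assumed counts and rates. The consequence falls mainly on later or ad hoc IDMC outputs.

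Reading the second vaccination as the second dose actually received would close the gap. A reader might then infer a second defect: the Day 57 injection, possibly Nimenrix, would be tabulated as post-dose 2, where the SAP does not separate the control products. The documents do not support that reading, because Protocol 9.1.3.2.1 ties Vaccination 2 to Day 29 and Vaccination 3 to Day 57. It is a reason to state the numbering, not a separate error.

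**What to change.** In SAP Table 2, keep the 28-day end of a post-dose period when the next scheduled dose is not given. Replace the Follow-up start rule with a definition of Follow-up as any time after first vaccination not covered by a post-dose period. The interval before a later administered dose then becomes Follow-up (non-active), which agrees with rule 1 for overlapping events, and the uncovered time falls to 0 days. Add that post-dose periods are numbered by scheduled dose, so that the Day 57 injection is always post-dose 3.

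The cost is two SAP sentences and a small change to the phase derivation program, which must allow Follow-up to consist of two separate intervals for one child. The change takes no position on whether dose 3 should be given after a missed dose 2; it only ensures that events are counted if it is.

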## **2.2. Pooling Algorithm for Analysis Centers**

Data will be pooled across the different centers.

## **2.3. Analysis Sets**

### **2.3.1. Full Analysis (FA) Set**

The FA set includes all subjects who were randomized and received at least one dose of study vaccine, regardless of the occurrence of protocol deviations. All safety analyses will be based on the FA set.

## **2.4. Definition of Subgroups**

No subgroup analysis is planned for this study.

## **3. SUBJECT INFORMATION**

Subject information will be analyzed based on the FA analysis set.

### **3.1. Demographics and Baseline Characteristics**

The following demographic and baseline characteristics will be summarized:

- Sex (Female/Male)
- Age (months)
- Race
- Ethnicity
- Weight (will only be listed)
- Height (will only be listed)
- Weight for age percentile
- Length for age percentile
- Breastfeeding history
- Family members smoking history
- Number and age of siblings (will only be listed)

### **3.2. Disposition Information**

The number and percentage will be tabulated for subjects that were:

- Screened
- randomized and vaccinated

- randomized not vaccinated
- not randomized but vaccinated
- not randomized, not vaccinated

Number and percentage of subjects who discontinued together with the reason(s) for discontinuation will be tabulated. This will be done separately for discontinuation of the study vaccine and for discontinuation of the trial.

### 3.3. Concomitant Medication

The analysis of concomitant therapies will be done using the World Health Organization (WHO) drug coded terms.

There will be special attention to any systemic use of analgesics/antipyretics, administered during 8 days following each vaccination (00:00 of day of vaccination + 7 days). The following CMCLASCD (ATC/DD codes) will be used for this: N02A (OPIOIDS) and N02B (OTHER ANALGESICS AND ANTIPYRETICS), M01A (ANTIINFLAMMATORY AND ANTIRHEUMATIC PRODUCTS, NON-STEROIDS) and M01B (ANTIINFLAMMATORY/ANTIRHEUMATIC AGENTS IN COMBINATION). The classes will be added in a footnote in all related tables and listings.

Concomitant therapies will be reported in each applicable period based on their start and stop date. That is, a concomitant therapy will be allocated to each period in which it was taken.

If a concomitant therapy record has missing components of its start and/or stop dates (missing day and/or month and/or year):

- In case of partial start or stop dates, the concomitant therapy records will be allocated to periods using the available partial information, without imputations. If, for example, only month and year are available, these will be compared to the month and the year of the periods, and the concomitant therapy record will be allocated to the period(s) where these date parts match. This rule may lead to assignment to multiple periods.
- In case of a completely missing start date, the concomitant therapy will be considered as having started before the trial.
- In case of a completely missing end date, the concomitant therapy will be considered as ongoing at the end of the trial.

Concomitant therapies will be tabulated per period.

